5.2 Hematologic Toxicity

The dose of Pegylated interferon will be reduced for any of the following toxicities:

- Grade 4 decreased neutrophil count (neutropenia) > 5 days duration
- Grade 4 decreased platelet count (thrombocytopenia) > 5 days duration
- ≥ 2 platelet transfusions per cycle for platelet counts < 30,000/ μ L
- ≥ 14 day delay in starting subsequent cycles due to low ANC (< 1,000/ μ L or low platelet count (less than 100,000/ μ L.)

Patients who experience hematologic toxicity should have appropriate laboratory testing at least weekly until the toxicity has resolved.

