7.1 Required Clinical, laboratory and Disease Evaluations

All baseline studies must be performed within **14 days** prior to enrollment and MRI of brain and/or spine within **30 days** prior to enrollment. **Obtain other studies prior to start of subsequent cycles and as otherwise indicated.**

STUDIES TO BE OBTAINED	Pre-study ¹ (Baseline)	Prior to Each Cycle	Q2 weeks Cycle 1	Prior to cycle 4,7,10,13 16,19,22,25	Every six months	When patient is removed from protocol Therapy**
History	X	X	X			X
Physical Exam with neurological exam (Wt, Ht and VS)	X	X	X			X
Performance Status	X	X				X
CBC, platelets and differential	X	X	X ⁵			X
CMP, magnesium phosphorous, calcium, Uric acid	X	X	X ⁵			X
PT, PTT	X					
AM cortisol, Free T4, TSH, (growth hormone if clinically indicated)	X				X	X
Urinalysis / urine dipstick	X			X		X
Urine or serum pregnancy test	X ²					
MRI of brain w/wo contrast	X ³			X		X
MRI spine	X ⁴			X ⁶		X
LP for CSF cytology	X ⁹			X ¹⁰		
Ophthalmology Evaluation ⁷	X				X	X
QOL questionnaire ⁸	X			X		X
Pegylated interferon Diary		X	X			X
Assessment of clinical toxicity/adverse events						X

1-Must be performed within 14 days prior to receiving the study drug with the exception of MRI of brain and spine. MRI of the brain and or spine can be done in within **30 days** prior to enrollment.

2-Required for all females of childbearing potential as a baseline study, then continue to follow institutional guidelines regarding pregnancy testing.

3- With and without contrast; within **30 days** prior to enrollment.

4-For patients with a known history of spinal disease, within **30 days** prior to enrollment on the study or when it is clinically indicated by the treating physician.

5-If no > Grade I toxicity during the previous cycle, then every month in subsequent cycles through cycle 27.

6-For patients with history of spinal disease; obtained at the same time points as MRI brain until no evidence of disease on 2 consecutive spine MRIs. Also when patient is removed from protocol therapy.

7-Ophthalmology evaluation only needed for patients with optic pathway gliomas. (Sooner than interval designated if indicated by neuro-ophthalmologist/ophthalmologist)

8- Children younger than 7 years and older will complete the parent survey only. For any child older than 7 years will complete also the patient questionnaire for Quality of life. QOL questionnaires are only available for English speaking patients. They have not been validated in other languages.

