9- LP only if there is evidence of tumor dissemination on spine MRI.

10-Repeat only if cytology showed tumor cells at study entry, until you have 2 consecutive negative cytologies.

** To be completed when patient comes off therapy unless it has been completed within the last 14 days and no toxicity greater than grade 1 was found.

This table only includes evaluations necessary to answer the primary and secondary aims. Obtain other studies as indicated for good clinical care.

History and Physical Examination: This should include signs and symptoms caused by the tumor/cancer, and determination of performance status or Lanski score. Patients must have a baseline neurological exam and neurological exam at the start of each new cycle. Weight, height and VS must be recorded.

Laboratory Evaluation:

-Hematology: Complete blood count, differential and platelet count every 2 weeks during the first cycle. If the patient does not experience any >Grade 1 hematologic toxicity during the first cycle, a CBC can be performed every 4 weeks on subsequent cycles, and as clinically indicated. If a patient experiences >Grade 1 hematologic toxicity (except for lymphopenia), they will continue to have weekly lab work until they have a cycle with no >Grade 1 toxicity. Following that cycle the lab work will be performed every 4 weeks (+/- 5 days) and as clinically indicated until completion of therapy. If the patient remains on-study beyond this and is hematologically stable, the patient will require lab work prior to every cycle as long as there is no >Grade 1 hematologic toxicity.

-Chemistries: CMP, magnesium, phosphorous, calcium and uric acid every other week during the first cycle. If the patient does not experience any >Grade 1 laboratory toxicity on the first cycle which is possibly, probably, or definitely related to Pegylated interferon, these can be performed every month on subsequent cycles, and as clinically indicated. If a patient experiences >Grade 1 laboratory toxicity they will continue to have weekly lab work until they have a cycle with no >Grade 1 toxicity. Following that cycle the lab work will be performed every 4 weeks and as clinically indicated until end of therapy.

If the patient remains on-study beyond this, the patient will require lab work prior to every cycle as long as there are no >Grade 1 laboratory toxicities.

-Calcium, phosphorous, magnesium and uric acid will be performed prior to each cycle and as clinically indicated.

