9.8 Analysis of Toxicity

Estimates will be obtained using life-table methods, with an event defined as the first occurrence of a primary toxicity. Time scale used in the time to first occurrence of a key acute and subacute toxicity is time in days since the start of therapy. Patients who have progression or recurrence of disease will be censored in these analyses. The rates of individual toxicities in each course of treatment, the number of patients who require a dose reduction and number of patients who come off protocol therapy due to toxicity will be summarized using standard descriptive statistical methods. To evaluate hematologic toxicity of long term Pegylated interferon administration adverse event data will be collected using CTCAE version 5.0 toxicity coding. Grade 3 or greater hematologic toxicities will be recorded per reporting period.

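### Section 9.8 reports toxicity rates by course, but the Section 7.1 schedule looks harder in cycle 1 and then by toxicity history, so rates of short laboratory toxicities can shift without any change in risk

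*Combined protocol and SAP*

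**What the plan says.** **Analysis.** Section 9.8 plans a descriptive summary of "The rates of individual toxicities in each course of treatment". It also plans a time-to-event summary: "Estimates will be obtained using life-table methods, with an event defined as the first occurrence of a primary toxicity". Both draw on the same visits and samples. The section says nothing about unequal frequency of assessment. Objective 1.2.2 is to define the toxicities of long-term weekly treatment.

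**Schedule in Section 7.1.**
- Cycle 1, blood counts: "Complete blood count, differential and platelet count every 2 weeks during the first cycle".
- Cycle 1, chemistries: "CMP, magnesium, phosphorous, calcium and uric acid every other week during the first cycle". History and examination are also marked 2-weekly in cycle 1 in the schedule table.
- Later cycles, no toxicity above Grade 1: "a CBC can be performed every 4 weeks on subsequent cycles, and as clinically indicated". Chemistries become monthly on a similar condition. Footnote 5 to the table says: "If no > Grade I toxicity during the previous cycle, then every month in subsequent cycles through cycle 27".
- After toxicity above Grade 1: "they will continue to have weekly lab work until they have a cycle with no >Grade 1 toxicity". Section 5.2 adds: "Patients who experience hematologic toxicity should have appropriate laboratory testing at least weekly until the toxicity has resolved".
- Visits after cycle 1 are once per cycle for everyone (Sections 4.1 and 7.1).

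**Therapy delivery map in Section 4.3.** The map is stated to cover all cycles. Its note to item a (blood count with differential) calls for weekly sampling, with no condition on cycle or earlier toxicity. There is no such note for chemistries. Item h, the toxicity and adverse event assessment, is listed at every cycle except cycle 13.

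**The concern.** A by-course table invites the reader to look along the courses and ask whether toxicity fades, persists or accumulates over 26 cycles. That reading needs a comparable chance of detecting an event in each course. Under Section 7.1 the chance differs in two ways: course 1 has twice the scheduled looks of later courses in clean patients, and from course 2 onward a patient with recent toxicity has four times the laboratory looks of a clean patient.

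A drop after course 1 could then be taken for tolerance when it reflects fewer samples. Silent laboratory toxicity is most exposed, because symptoms are also recorded in the patient diary throughout. Chemistries matter here: the side-effect table in Section 6.1 places irritation of the liver in its common column, and it is the chemistry panel that detects it.

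**Working it through.** The plan gives no expected toxicity rate by course, so there is no figure to reproduce. The check asks how far the observed rate can move when the true risk is held constant.

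**Inputs from the documents.** Cycle length is 28 days (Section 4.3). Laboratory looks per cycle under Section 7.1 are 28/14 = 2 in cycle 1, then 28/28 = 1 if clean or 28/7 = 4 after toxicity above Grade 1. Visits are 2 in cycle 1, then 1.

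**Assumptions not in the documents.** The true risk q is the same in every course (20%, varied from 10% to 40%). An abnormality lasts D days (5 to 28) and starts at a random time. Any detected event moves the patient to weekly sampling in the next course, and a course without one returns the patient to 4-weekly sampling.

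**Chance of detection** with samples s days apart: d = min(1, D/s).

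**Observed rate in course 1:** q × d14.

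**Observed rate later.** Let w be the share of patients on weekly sampling. The observed rate is r = q × [w × d7 + (1 − w) × d28]. Once stable, w = r, so r = q × d28 / [1 − q × (d7 − d28)].

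For D = 7 and q = 20%: course 1 is 0.20 × 0.50 = 10%. Later, r = 0.05 / (1 − 0.15) = 0.05/0.85 = 5.9%.

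Results for q = 20% and patients of equal risk:

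| D (days) | d7 | d14 | d28 | Course 1 | Later |
|---|---|---|---|---|---|
| 5 | 71% | 36% | 18% | 7.1% | 4.0% |
| 7 | 100% | 50% | 25% | 10.0% | 5.9% |
| 10 | 100% | 71% | 36% | 14.3% | 8.2% |
| 14 | 100% | 100% | 50% | 20.0% | 11.1% |
| 28 | 100% | 100% | 100% | 20.0% | 20.0% |

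For D = 7, varying the true risk:
- q = 10%: 5.0% in course 1, then 0.025/(1 − 0.075) = 2.7%.
- q = 40%: 20.0% in course 1, then 0.10/(1 − 0.30) = 14.3%.

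**Patients who differ in risk.** A simulation of the same schedule, with individual risks drawn from a beta distribution, compares course 1 with course 8:
- mean risk 20%, D = 7: 9.9% and 8.5%;
- mean risk 20%, D = 14: 19.9% and 13.4%;
- mean risk 40%, D = 7: 19.9% and 20.1%.

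In the last case, denser sampling of high-risk patients offsets sparser sampling of the rest. The flat line is a cancellation of two distortions and does not show that detection was even.

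**Who supplies the later events.** For D = 7, q = 20% and equal risk, w = 5.9%. These patients supply 0.059 × 0.20 = 0.0118 of a total of 0.0588, which is 20% of detected events from about 6% of patients.

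**One common sample per course.** With a single end-of-course sample in every patient, the same case gives 0.20 × 0.25 = 5% in every course, including the first. The level is lower, but the drift is gone.

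**The case against.** The strongest objection is the map note. If weekly blood counts apply in all cycles, sampling for hematologic toxicity neither halves nor depends on earlier toxicity, and hematologic toxicity is the type that Section 9.8 singles out for long-term evaluation. This stands as far as it goes: under that reading the point fails for blood counts. It does not reach chemistries, history or examination, which have no such note. The documents also do not say which blood-count instruction governs, so an analyst cannot tell which schedule produced the data.

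Second, the analysis is descriptive. No test or trend across courses is planned, extra tests may be done when clinically indicated, and the side-effect diary runs through every cycle. This limits the consequences, especially for symptoms, but does not make the columns of a by-course laboratory table comparable.

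Third, risk and duration are assumed. The drug is given weekly without breaks, and nothing in the documents shows that abnormalities are brief or randomly timed. That is correct, and the size is therefore an illustration only.

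A reader might also infer stronger claims that the documents do not support:
- That rates must fall, or must halve. The 2:1 ratio holds for durations up to 14 days only in patients who stay on 4-weekly sampling. Overall the illustration is 10% against about 6%, and it can be nil.
- That later courses are dominated by intensively sampled patients. They are over-represented, but clean patients still supply about 80% of detected events in the illustration.
- That visits become weekly after toxicity. Only laboratory tests do.

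**Conclusion.** The point holds in limited form. Under Section 7.1 the intensity of assessment changes after cycle 1 and then depends on earlier toxicity, and Section 9.8 does not allow for it. By-course rates of short, laboratory-detected toxicities can therefore change after course 1 with no change in true risk.

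The size cannot be derived from the documents. At an assumed constant 20% risk in patients of equal risk, the change runs from 7.1% to 4.0% for 5-day abnormalities, through 20% to about 11% for 14-day abnormalities, to none for those lasting a full cycle. It may cancel when patients differ in risk. For blood counts it depends on which of two conflicting instructions is followed. The primary endpoint is untouched; what is at stake is the reading of a descriptive secondary result in about 17 patients.

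The missing item h at cycle 13 is a separate, small inconsistency. History, examination, laboratory tests and diary are still listed there, so its effect on the rates is likely to be slight.

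**What to change.** 1. **Section 9.8.** Keep the all-sample rates by course. Beside them, report by-course laboratory toxicity rates from the first scheduled end-of-course sample, at about Day 29 and before any delay or repeat test. Do not use the later sample that qualifies the patient for the next cycle: Section 4.3 requires ANC of at least 1,000/μL and platelets of at least 100,000/μL to start, so that sample cannot show counts below those limits. Give the number of samples per course, and show separately the events found only on extra samples. Keep all samples for safety decisions and for the proportion of patients who ever have each toxicity.
2. **Blood-count schedule.** Reconcile the map note in Section 4.3 with the text and footnote 5 of Section 7.1. The Section 7.1 text also needs clarifying, since it has patients continue weekly tests although cycle 1 testing is 2-weekly.
3. **Cycle 13.** Reconcile the map entry with the other cycles and with the Section 7.1 table. In the copy read, that table marks toxicity assessment only at removal from therapy, though marks may have been lost in extraction.

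The cost is a few sentences, one extra descriptive table and two schedule clarifications. The added rates will be lower than the all-sample rates, so the table should say why. Item 1 works whichever blood-count schedule is adopted, because both provide a blood count and chemistries before each cycle.

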9.9 Subject Accrual

Subjects of both genders, from all racial and ethnic groups are eligible for this study if they meet the criteria outlined in Section 3.2. To date, there is no information that suggests differences in drug metabolism or disease response would be expected in one group compared to another. Efforts will be made to extend this accrual to a representative population, but in this study, a balance must be struck between patient safety considerations and limitations on the number of individuals exposed to potentially ineffective treatments on the one hand and the need to explore gender and ethnic aspects of clinical research on the other hand. If differences in outcome that correlates to gender or to ethnic identity are noted, accrual may be expanded or additional studies may be performed to investigate those differences more fully.

9.10 Radiographic Evaluation

MRI of brain with and without contrast must be performed within **30 days** prior to enrollment on the study. Patients will undergo baseline and follow-up imaging in the same scanner if possible. All patients will receive a standard MRI, unless contraindicated, performed on either the 1.5T or 3T scanner. (If MRI is contraindicated, patient cannot be enrolled). Patients undergoing MRI may also undergo additional MR sequences such as dynamic contrast-enhanced (DCE) or MRI, dynamic susceptibility contrast (DSC) MRI as time permits. These sequences are part of standard brain tumor protocols. Percent agreement between the sequences will be estimated as the number of follow-up scans in which the corresponding sequence agreed divided by the total number of follow-up scans. Standard error will be estimated by use of the bootstrap method 26 to account for the correlated dependent response data, and these values will be used to estimate the 95% confidence intervals. The event-free survival distributions will be compared across the MR sequences, with a proportional hazards model developed for dependent survival data by Wei et al (1989).

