1.2 SECONDARY STUDY OBJECTIVES

1.2.1

To estimate event free survival (EFS) (based on standard two or three-dimensional tumor measurements) for children with recurrent, refractory or progressive Juvenile Pilocytic Astrocytomas and Optic Pathway Gliomas who are treated with Peginterferon.

1.2.2

To define the toxicities of long term weekly pegylated interferon alpha-2b in pediatric patients with refractory, recurrent and progressive Juvenile Pilocytic Astrocytomas and Optic Pathway Gliomas.

1.2.3

To compare response categories and EFS across the 3 MR sequences (T2-weighted, FLAIR, T1-weighted post-contrast).

1.2.4

To evaluate the quality of life for patients with recurrent, refractory and progressive Juvenile Pilocytic Astrocytomas and Optic Pathway Gliomas who receive therapy with pegylated interferon alpha-2b

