9.0 STATISTICAL CONSIDERATIONS

9.1 Sample Size and Study Duration

This study will enroll patients without NF-1 and patients with NF-1. Based on the established accrual goals and incidence of pediatric low grade gliomas 17 patients can be accrued within 36 months of protocol activation, given an average of 1 patient per 2.1 months. Assuming 15% of patients are not evaluable or eligible, 20 patients total will be required to be enrolled on this study.

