9.2 Study Design

The study is designed using Simon's two stage optimal design with a power of 80% and an alpha error of 5%. We assume an uninterested response rate of 5% and the promising response rate is 25%. In the first stage of the study, 9 eligible patients will be enrolled. If none responder among the 9 patients, the study terminates and treatment will be determined to have no improvement in the response rate. Otherwise, the study will continue with the second stage in which 8 additional eligible patients will be enrolled for a total of 17 eligible patients. At the end of total patient accrual, at least 3 of 17 eligible patients must

achieve response in order to consider the treatment interesting for further evaluation. Response is considered as either CR or PR or SD.

Optimal Two Stage Design	Optimum Design
First Stage Sample Size (n1)	9
Upper Limit For 1st Stage Rejection of Drug (r1)	0
Maximum Sample Size (n)	17
Upper Limit for 2nd Stage Rejection of Drug (r)	2
Expected Sample Size If Response Probability = P0	11.96
Probability of Early Termination at P0	0.63

9.3 Methods of Analysis:

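### The 95% intervals planned for agreement between MR sequences would cover less than 95%: moderately less with 17 patients and agreement of 60–80%, much less near full agreement or with 9 patients

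*Combined protocol and SAP*

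**What the plan says.** Secondary objective 1.2.3 is "To compare response categories and EFS across the 3 MR sequences (T2-weighted, FLAIR, T1-weighted post-contrast"). Section 9.10 holds the whole agreement analysis:

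- **Estimator:** "Percent agreement between the sequences will be estimated as the number of follow-up scans in which the corresponding sequence agreed", over all follow-up scans.
- **Standard error:** "Standard error will be estimated by use of the bootstrap method 26 to account for the correlated dependent response data".
- **Interval:** "these values will be used to estimate the 95% confidence intervals".

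The section does not state the quantile, the scale, whether patients or scans are resampled, or whether agreement is pairwise or across all three sequences. It gives no rule for the case where every scan agrees. The method citation is number 26, but the reference list ends at 18, so the citation does not fill these gaps.

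The number of patients comes from Section 9.2: "In the first stage of the study, 9 eligible patients will be enrolled", then "8 additional eligible patients will be enrolled for a total of 17 eligible patients".

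**The concern.** An interval built from a standard error is most naturally read as estimate ± 1.96 SE. That form relies on a well-estimated SE and a roughly symmetric sampling distribution. A proportion that may lie near 1, from repeated scans in 9 or 17 patients, offers neither. The SE shrinks as the estimate approaches 100%, the upper limit can pass 100%, and when every scan agrees the interval is a single point.

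At stake is how firmly the trial can say that T2, FLAIR and post-contrast T1 give the same response category. Intervals that are too narrow would overstate how well agreement is known. A second, smaller question is how to read the percentage itself, since sequences that both call most scans stable disease (SD) agree often whether or not they track the same changes.

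**Working it through.** **The plan's own figures.** Section 9 gives no coverage or precision figure for agreement. The design figures that fix the number of patients do reproduce:
- Stage-one stop at a 5% response rate: 0.95^9 = 0.630 (plan: 0.63).
- Expected size: 9 + 8 × (1 − 0.6302) = 11.96 (plan: 11.96).
- Enrolment: 17 / 0.85 = 20 (plan: 20).
- Stage-one stop at a 25% response rate: 0.75^9 = 0.075. The 9-patient case is therefore likely for an inactive drug and unlikely for a promising one.

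**Inputs.** From the documents: 9 or 17 patients, and up to 8 scheduled follow-up MRIs (before cycles 4 to 25, Section 7.1), fewer after progression (Sections 4.3 and 8.1). Assumed, because not given: true agreement 60–95%, within-patient correlation (ICC) 0–0.5, and progression of 5%, 15% or 30% per scan.

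**One case by hand.** At 15% progression per scan, capped at 8 scans, the mean is (1 − 0.85^8)/0.15 ≈ 4.9 scans per patient. With ICC 0.3 the design effect is 1 + 3.9 × 0.3 = 2.17, ignoring unequal scan counts. At 95% agreement:
- 17 patients: 17 × 4.9 = 83.3 scans, effective size 83.3/2.17 = 38.4, or 1.9 effective disagreements. SE = √(0.95 × 0.05/38.4) = 0.035. Interval 88.1% to 101.9%.
- 9 patients: 44.1 scans, effective size 20.3, or 1.0 effective disagreement. SE = 0.048. Interval 85.5% to 104.5%.

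With one or two effective disagreements, the SE is poorly estimated and is smallest when the estimate is highest.

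**Simulation.** Agreement was beta-binomial within patient, with 1,500–2,000 trials per setting and 300–400 bootstrap samples. Monte Carlo error is about ±2 points: 1.96 × √(0.85 × 0.15/1500) = 0.018. Results at 15% progression per scan, for ICC 0.1 / 0.3 / 0.5:

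| Patients | True agreement | Coverage, ± 1.96 SE (%) | Zero width (%) | Coverage, Wilson with t (%) |
|---|---|---|---|---|
| 17 | 70% | 91.5 / 91.0 / 91.1 | 0 / 0 / 0 | 95.8 / 94.4 / 95.4 |
| 17 | 80% | 89.0 / 89.0 / 87.4 | 0 / 0 / 0.1 | 94.4 / 94.5 / 93.6 |
| 17 | 90% | 89.2 / 84.3 / 79.0 | 0.1 / 0.7 / 2.5 | 96.4 / 93.8 / 90.6 |
| 17 | 95% | 85.4 / 77.6 / 69.9 | 3.6 / 8.7 / 14.8 | 97.3 / 96.6 / 96.9 |
| 9 | 95% | 79.0 / 71.8 / 60.4 | 18.5 / 27.0 / 38.6 | 97.4 / 97.4 / 97.0 |

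In the 95% rows, the upper limit passed 100% in 57–79% of trials with 17 patients and 59–68% with 9.

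Over all settings, coverage of ± 1.96 SE was:
- 17 patients: 87–93% (agreement 60–80%) and 70–91% (90–95%).
- 9 patients: 81–91% and 60–87%.

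**Other readings of the text:**
- Percentile interval: 71–93% (17), 61–90% (9).
- t quantile on the raw scale: 71–94% (17), 61–94% (9).
- Scans resampled, ICC 0.3–0.5: 61–81% (17), 53–80% (9). With ICC 0, resampling scans does no harm.

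**Bounded interval.** Take n* = p(1 − p)/SE² with the patient-level SE, and compute the Wilson interval on n* with the t quantile on (patients − 1) degrees of freedom. In the 17-patient case above (n* = 38.4, t = 2.120) this gives 81.8% to 98.8%. Simulated coverage over all settings: 91–98% (17), 94–99% (9).

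**Chance agreement.** With equal category shares on two sequences, chance agreement is the sum of squared shares; SD/PR/PD of 80/10/10 gives 0.64 + 0.01 + 0.01 = 66%. Varying progression over 5–40% per scan and responders over 5–25%, the SD share runs from 48% to 91% and chance agreement from 37% to 84%. At observed agreement of 90%, kappa would be (0.90 − 0.37)/0.63 = 0.84 at one end and (0.90 − 0.84)/0.16 = 0.38 at the other.

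**The case against.** The strongest reply has four parts.

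- **The plan never says ± 1.96 SE.** True: that form is inferred. But a percentile interval or a t quantile on the raw scale also falls short, so leaving the form open does not rescue the stated method.
- **A reader might infer that coverage is far below 95% throughout.** The documents do not support that. They give no expected agreement, and Section 10.4 warns that enhancement varies from scan to scan in these tumors. Post-contrast T1 is one of the three sequences, so real disagreement is plausible. With 17 patients and 60–80% agreement the shortfall is moderate and zero-width intervals are essentially absent. This part stands.
- **A reader might infer that percent agreement is mostly chance matching on SD.** That rests on a category mix the documents do not give. The one benchmark cited for recurrent disease, 5-year PFS of 42.3% with vinblastine (Section 2.2), implies about 3.9% progression per 12 weeks if exponential. At 5% per scan, chance agreement is 62–84%. At 30–40% per scan it is 37–52%, and SD–SD matches account for only 23–44%. This part also stands.
- **Kappa is fragile at this size.** In a simulation with a 90/5/5 mix, true kappa 0.7 and independent scans, the 95% sampling range was 0.36–0.93 with 17 patients and 0–1 with 9. Kappa therefore cannot replace percent agreement.

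The analysis also carries no decision rule.

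**Conclusion.** The concern holds in a limited form. No reading of Section 9.10 that was tried (± 1.96 SE, t on the raw scale, percentile, or scans resampled where ICC is material) delivers its nominal 95% level reliably for this number of patients. Under the natural reading the shortfall is about 2 to 8 points with 17 patients and 60–80% agreement, and 4 to 25 points at 90–95%. With 9 patients it reaches about 35 points.

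These figures rest on assumed agreement, within-patient correlation and progression, and on a beta-binomial model. The direction was the same in every setting; the size was not. Chance-expected agreement should be reported and not presumed high. The effect stops at secondary objective 1.2.3, and the response rule in Sections 9.2 to 9.5 does not use this analysis.

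**What to change.** Amend Section 9.10 before the data are analyzed:

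1. Name the patient as the resampling unit, and say whether agreement is pairwise or three-way.
2. Replace the SE-based interval with a bounded small-sample one: Wilson on n* with a t quantile, as above. A logit interval with the same quantile and an exact bound at 100% is an alternative (coverage 93–98% with 17 patients, 95–99% with 9).
3. State a rule for 100% agreement, where the bootstrap SE is zero. One cautious choice counts each patient once and takes the exact lower limit 0.025^(1/n): 80.5% for 17 patients, 66.4% for 9.
4. Beside percent agreement, show the cross-table of response category by sequence and the chance-expected agreement from the observed shares. Keep SD separate from CR and PR in that table, because Sections 9.2 and 9.4 differ on whether SD counts as response and need reconciling.
5. Report any kappa as descriptive, with a patient-clustered interval.
6. Correct the citation number for the bootstrap method.

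The cost is a few sentences and a little code, with no new data. Intervals widen slightly: in one simulated setting (90% agreement, ICC 0.2, 17 patients) mean width rises from 0.17 to 0.20.
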